3. PATIENT SELECTION, ENROLMENT, RESTRICTIONS, DISCONTINUATION AND WITHDRAWAL

Each patient should meet all of the inclusion and none of the exclusion criteria for this study. These are designed in line with the EU approved indication for patients carrying *BRCA* mutated ovarian cancer. Under no circumstances can there be exceptions to this rule.

Patients with unknown germline *BRCA* mutation status, or patients found to carry *gBRCA*wt disease, or patients previously identified as having *BRCA*m disease based on a tumour test (with unknown *gBRCA* mutation status or with previously identified *gBRCA*wt status) will be considered for screening.

Patients previously diagnosed with gBRCAm disease will not be included in this study.

Patients with unknown *BRCA* mutation status who are considered for inclusion in this trial should be identified early so that the appropriate *BRCA* mutation screening procedures can be put in place in a timely manner.

In order to optimise the screening of patients and potential timely treatment initiation with study drug, patients may start the screening procedure from the end of cycle 3 of their current chemotherapy, if they are responding to treatment in the opinion of the investigator.

BRCA mutation status will be determined or confirmed through central blood and tumour testing as outlined in Figure 2 (see also Section 5.7.6).

Exploratory HRRm patient cohort

Patients screened for the study with unknown *BRCA* status or with known *gBRCA* status, for whom an adequate archival tumour tissue sample is available, will be tested for qualifying HRR gene alterations, as defined in Section 1.1.4.

Patients found not to carry a *BRCA* mutation in their tumour (tumour *BRCA*wt), and with qualifying *BRCA*-independent HRR genetic alterations will be included in the study (HRRm cohort), and analysed as a separate exploratory cohort.

Patients previously identified as having *BRCA*m based on a tumour test will not be screened for HRR gene mutations.

*Undetermined: the central tumour BRCA testing was unable to determine the presence or absence of BRCA mutation.

3.1 Inclusion criteria

Screening procedures described in Section 3 should be strictly complied with. For inclusion in the study patients should fulfil the following criteria:

- 1. Provision of informed consent prior to any study specific procedures
- 2. Age 18 years or over
- 3. Documented germline or somatic mutation in *BRCA1* or *BRCA2* genes that is predicted to be deleterious or suspected deleterious (known or predicted to be detrimental/lead to loss of function) [Genetic counselling for patients with germline BRCA mutations should be performed according to local regulations]

Or

Tumour *BRCA*wt status and documented qualifying mutation in any of 13 genes involved in the HRR pathway, excluding *BRCA1* and *BRCA2* (*ATM, BARD1, BRIP1, CDK12, CHEK1, CHEK2, FANCL, PALB2, PPP2R2A, RAD51B, RAD51C, RAD51D,* and *RAD54L*), identified by the Lynparza HRR Assay in archival tumour tissue (i.e., *BRCA*-independent HRRm)

- 4. Patients with platinum sensitive relapsed high grade epithelial ovarian cancers (including primary peritoneal and/or fallopian tube cancer):
 - Platinum sensitive disease is defined as disease progression ≥6 months after completion of their last dose of platinum based chemotherapy
- 5. Patients should have received at least 2 previous lines of platinum containing therapy prior to enrolment:
 - For the last chemotherapy course immediately prior to enrolment on the study, patients must be, in the opinion of the investigator, in response (partial or complete radiological response) and no evidence of a rising CA-125, following completion of this chemotherapy course.
- 6. Patients must have normal organ and bone marrow function measured within 28 days of enrolment, as defined below:
 - Haemoglobin \ge 10.0 g/dL with no blood transfusions in the past 28 days
 - Absolute neutrophil count (ANC) $\ge 1.5 \times 10^9/L$
 - Platelet count $\geq 100 \text{ x } 10^9/\text{L}$
- 7. Total bilirubin ≤ 1.5 x institutional upper limit of normal (ULN), Aspartate aminotransferase (AST) (Serum Glutamic Oxaloacetic Transaminase [SGOT]) / Alanine aminotransferase (ALT) (Serum Glutamic Pyruvate Transaminase [SGPT]) ≤ 2.5 x institutional ULN unless liver metastases are present in which case they must be ≤ 5x ULN
- 8. Creatinine clearance > 50 ml/min (calculated)
- 9. Patients must be postmenopausal or have evidence of non-childbearing status for women of childbearing potential.

Postmenopausal is defined as any of the following:

- Amenorrhoea for 1 year or more following cessation of exogenous hormonal treatments
- For women under 50 years old, luteinizing hormone (LH) and follicle stimulating hormone (FSH) levels in the post-menopausal range
- Radiation-induced oophorectomy, with interval of 1 year or more since last menses

- Chemotherapy-induced menopause, with interval of 1 year or more since last menses
- Surgical sterilisation (bilateral oophorectomy or hysterectomy).

3.2 **Exclusion criteria**

Screening procedures described in Section 3 should be strictly complied with and patients should not enter the study if any of the following exclusion criteria are fulfilled:

- 1. Patients previously diagnosed with gBRCAm disease
- 2. Participation in another clinical study with an investigational product during the most recent chemotherapy course
- 3. Patients with a known hypersensitivity to olaparib or any of the excipients of the product
- 4. Patients receiving any systemic chemotherapy or radiotherapy (except for palliative reasons) or major surgery within 3 weeks prior to olaparib treatment. Major surgery within 3 weeks of starting study treatment and patients must have recovered from any effects of any major surgery
- 5. Persistent toxicities Common Terminology Criteria for Adverse Event (CTCAE) grade 2 caused by previous cancer therapy, excluding alopecia
- 6. Patients with myelodysplastic syndrome/acute myeloid leukaemia
- 7. Immuno-compromised patients e.g., Human Immunodeficiency Virus (HIV) requiring treatment or active Hepatitis B or C
- 8. Patients with symptomatic uncontrolled brain metastases. The patient can receive a stable dose of corticosteroids before and during the study as long as these were started at least 4 weeks prior to treatment. Patients with spinal cord compression unless considered to have received definitive treatment for this and evidence of clinically stable disease (SD) for 28 days
- 9. Patients considered to be at a high medical risk due to a serious, uncontrolled medical disorder, systemic disease or active, uncontrolled infection
- 10. Currently pregnant (confirmed with a positive pregnancy test) or breastfeeding.

Procedures for withdrawal of incorrectly enrolled patients see Section 3.4.

3.3 **Patient enrolment**

Investigator(s) should keep a record of the patient screening log, of patients who entered prestudy screening. The Investigator(s) will:

- Obtain signed informed consent from the potential patient before any study specific procedures are performed.
- Assign potential patient a unique enrolment number, beginning with 'E#'. This number is obtained through Interactive Voice/Web response System (IVRS/IWRS).
- Determine patient eligibility. See Section 3.
- If patient meets eligibility criteria enrol patient through IVRS/IWRS to dispense the IP.

If a patient withdraws from participation in the study, then her enrolment number cannot be reused.

3.4 **Procedures for handling incorrectly enrolled patients**

Where a patient does not meet all the eligibility criteria but is incorrectly enrolled and started on treatment, the Investigator should inform the AstraZeneca study physician immediately, and a discussion should occur between the AstraZeneca study physician and the Investigator regarding whether to continue or discontinue the patient from treatment. The AstraZeneca study physician must ensure all decisions are appropriately documented.

3.5 **Methods for assigning treatment groups**

Not applicable.

3.6 **Methods for ensuring blinding**

Not applicable.

3.7 Methods for unblinding

Not applicable.

3.8 **Restrictions**

Patients of childbearing potential and their partners, who are sexually active, must agree to the use of two highly effective forms of contraception in combination throughout the period of taking treatment and for at least one month after last dose of study drug.

For details refer to Appendix E.

3.9 **Discontinuation of investigational product**

Patients may be discontinued from investigational product (IP) in the following situations:

- Patient decision. The patient is at any time free to discontinue treatment, without prejudice to further treatment
- Adverse Event
- Bone marrow findings consistent with myelodysplastic syndrome (MDS)/acute myeloid leukaemia (AML)
- Severe non-compliance with the study protocol
- Disease progression (unless in the investigator's opinion the patient is benefiting from the treatment and does not meet any other discontinuation criteria)

3.9.1 **Procedures for discontinuation of a patient from investigational product**

By discontinuing from IP, the patient is not withdrawn from the study unless the patient withdraws consent to participation in the study. If a patient is withdrawn from study, see Section 3.10.

At any time, patients are free to discontinue investigational product or withdraw from the study, without prejudice to further treatment. A patient that decides to discontinue IP will always be asked about the reason(s) and the presence of any adverse events. Any patient discontinuing IP should be seen at 30 days post last dose of IP for the evaluations outlined in the study schedule. After discontinuation of IP, the Principal Investigator (PI)/Sub-Investigator will perform the observation(s), test(s) and evaluation(s) consistent with the current standard of care as well as give appropriate medication and all possible measures for the safety of the patient. Patients who discontinue treatment prior to documented progression should continue to be followed for first progression as per the protocol recommended schedule. In addition, they will record on the electronic case report form (eCRF) the date of discontinuation. If patients discontinue olaparib, the study monitor must be informed immediately. Patients will be required to attend the treatment discontinuation visit. The patient should return all IP.

After discontinuation of olaparib at any point in the study, all ongoing AEs or SAEs must be followed until resolution unless, in the investigator's opinion the condition is unlikely to resolve due to the patients underlying disease, or the patient is lost to follow up (see Section 4.3.1). All new AEs and SAEs occurring during the 30 calendar days after the last dose of olaparib must be reported (if SAEs, they must be reported to AstraZeneca within 24 hours as described in Section 6.5) and followed to resolution as above. Patients should be seen at least 30 days after discontinuing the last IP dose to collect and / or complete AE information. Any untoward adverse event occurring subsequent to that the investigator assesses as possibly related to the study medication should also be reported as an adverse event. Cases of MDS, AML or new primary cancers, as well as pneumonitis should be reported also after the 30-day follow-up AE reporting period.

Any patient who has not yet shown disease progression at withdrawal from IP should continue to be followed as detailed in Table 3.

All patients should be followed for survival, up to the final analysis.

3.10 **Criteria for withdrawal**

3.10.1 Screen failures

Screening failures are patients who do not fulfil the eligibility criteria for the study, and therefore must not be enrolled. These patients should have the reason for study withdrawal recorded as 'Did not meet Eligibility Criteria' (i.e., patient does not meet the required inclusion/exclusion criteria), and screening failure/ study withdrawal should be noted in IVRS/IWRS. This reason for study withdrawal is only valid for screen failures (not enrolled patients). Patients who were screen failures may be re-enrolled and re-screened if in the opinion of the Investigator, the reason(s) for earlier withdrawal no longer applies. Patients cannot re-enter the study if dosed and subsequently withdrawn from the study.

3.10.2 Withdrawal of the informed consent

Patients are free to withdraw from the study at any time (investigational product and assessments), without prejudice to further treatment.

A patient who withdraws consent will always be asked about the reason(s) and the presence of any adverse events (AE). The Investigator will follow up AEs outside of the clinical study.

If a patient withdraws from participation in the study, then her unique enrolment number cannot be reused. Withdrawn patients will not be replaced.

3.11 Discontinuation of the study

The study may be stopped if, in the judgment of AstraZeneca, trial patients are placed at undue risk because of clinically significant findings that are not considered to be consistent with continuation of the study.

Regardless of the reason for termination, all data available for the patient at the time of discontinuation of follow-up must be recorded in the eCRF. All reasons for discontinuation of treatment must be documented.

In terminating the study, the Sponsor will ensure that adequate consideration is given to the protection of the patients' interests.

4. **STUDY PLAN AND TIMING OF PROCEDURES**

Table 1Study Schedule Screening

	Part 1	Part 2
	BRCA testing	Patients with known tumour BRCA mutation
	Post-cycle 3 of ongoing chemotherapy to -28 days ^a	-28 to -1 days
Informed consent	X^b	X ⁱ
Demographics		Х
Medical and surgical history		Х
Inclusion/exclusion criteria		Х
ECOG Performance Status (0-2)		Х
Vital signs, body weight, (includes blood pressure [BP] and pulse)		Х
Haematology / clinical chemistry ^c		Х
Pregnancy test		Х
Tumour Assessment (CT or MRI according to RECIST 1.1 guidelines) ^d		Х
Blood sample for disease specific marker (CA-125)		Х
Tumour sample for determination of tumour BRCA status	X ^e	X ^e
Blood sample for determination of gBRCA status	\mathbf{X}^{f}	X ^f
Tumour sample for HRR testing	X ^g	
Adverse Events (from time of consent)	X^h	X ^h
Relevant concomitant medications		Х
Optional tumour sample for exploratory analysis		X ^j

a The post cycle 3 of ongoing chemotherapy to -28 day time period is to allow patients with unknown *BRCA* mutation status who are considered for inclusion in this trial to be identified early so that the appropriate *BRCA* mutation screening procedures can be put in place in a timely manner. In order to optimize the screening of patients and potential timely treatment initiation with study drug patients may start the screening procedure from the end of cycle 3 of their current chemotherapy if they are, in the opinion of the investigator, in partial or complete response.

b Informed consent for *BRCA* testing and HRR testing only.

c Coagulation tests will only be required if clinically indicated.

d Computed Tomography (CT)/ Magnetic Resonance Imaging (MRI) of the chest, abdomen and pelvis not more than 28 days prior to starting olaparib and as close as possible to the start of olaparib.

e

- As part of the study screening procedures, an archival tumour sample should be provided for central determination or confirmation of *BRCA*m status. If an archival tumour sample is not available, a fresh biopsy should be provided (see Sections 5.7.1 and 5.7.6 for further details).
 - For patients with unknown *BRCA*m status and patients with previously identified g*BRCA*wt status, tumour *BRCA*m status will be determined by central laboratory testing on tumour samples.
 - Patients who have been previously identified as having *BRCA* mutations in the tumour, determined in a local test, can enter screening Part 2; however confirmatory central test from tumour should be completed prior to enrolment.
- f Blood samples for central determination of gBRCA status will be collected from patients who are found to carry a tumour BRCA mutation based on the central tumour test (see Sections 5.7.4 and 5.7.7).
 - This result will be used to confirm patients' germline or somatic *BRCA* mutated disease, and the test should be completed prior to study enrolment.
 - Patients who have been previously identified as having *BRCA* mutations in the tumour and enter the study at Part 2 screening as either known somatic patients based on the local testing, or tumour *BRCA* with unknown germline status, can be enrolled into the study after central confirmation of their *BRCA* tumour mutation status and blood sample collection for central confirmation of the germline or somatic *BRCA* mutation status.
- g As part of the study screening procedures, if available, an archival tumour sample should be provided for central determination of *BRCA*-independent HRR mutation status. If an adequate archival tumour sample is not available for this test, it will not be conducted (see Section 5.7.2 for further details).
- h Only SAE's related to screening procedures will be collected at this visit.
- i Informed consent for participation in the main study, including optional consent for tumour and blood samples for exploratory analysis.
- j All patients are requested to provide samples of their most recently available tumour tissue for exploratory testing (optional and subject to specific informed consent). This is to be provided in addition to the diagnostic samples for tumour *BRCA* and HRR testing (see Section 5.7.3).

Study Schedule – On Study Treatment and Discontinuation

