6.4.1 Time period for collection of adverse events

Adverse Events, including Serious Adverse Events, will be collected from time of signature of informed consent, throughout the treatment period and up to and including the 30-day follow-up period*. All ongoing and any new AEs/SAEs identified during the 30 calendar days follow up period after last dose of study medication must be followed to resolution. After any interim analysis, any ongoing AEs/SAEs need to be unlocked and followed for resolution.

*Exception: In screening part 1 only SAEs related to study procedures must be reported (AEs do not require reporting). From screening Part 2 onwards - all AEs/SAEs must be reported.

In cases where any transfusions to manage anaemia and or thrombocytopenia are needed, these should be recorded with date, type and units given.

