6.4.10 Lack of efficacy

When there is deterioration in the ovarian cancer, for which the study treatment(s) is being used, there may be uncertainty as to whether this is lack of efficacy or an AE. In such cases, unless the Sponsor or the reporting physician considers that the study treatment contributed to the deterioration of the condition, or local regulations state to the contrary, the deterioration should be considered to be a lack of efficacy and not an AE.

6.4.11 **Deaths**

All deaths that occur in screening Part 1 related to study procedures should be reported as a SAE.

All deaths that occur during the study, or within the protocol defined 30 day post study follow up period after the administration of the last dose of study treatment, must be reported as follows:

- Death clearly the result of disease progression should be reported to the study monitor at the next monitoring visit and should be documented in the eCRF but should not be reported as an SAE.
- Where death is not due (or not clearly due) to progression of the disease under study, the AE causing the death must be reported to the study monitor as a SAE within 24 hours (see Section 6.2 for further details). The report should contain a comment regarding the co-involvement of progression of disease, if appropriate, and should assign main and contributory causes of death. This information can be captured in the 'Death eCRF'.
- Deaths with an unknown cause should always be reported as a SAE. A post mortem maybe helpful in the assessment of the cause of death, and if performed a copy of the post-mortem results should be forwarded to AstraZeneca within the usual timeframes.

6.5 **Reporting of serious adverse events**

In screening Part 1, only SAEs related to study procedures must be reported. From screening Part 2 onwards, all SAEs have to be reported, whether or not considered causally related to the investigational product, or to the study procedure(s). All SAEs will be recorded in the CRF.
If any SAE occurs in the course of the study, then investigators or other site personnel inform the appropriate AstraZeneca representatives immediately, but **no later than 24 hours** of when he or she becomes aware of it.

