Patients who are taking warfarin or acenocoumarol may participate in this trial; however, it is recommended that prothrombin time (international normalised ratio [INR] and activated partial thromboplastin time [APTT]) be monitored at baseline if patients are on anticoagulation at enrolment and repeat as per local guidelines for the anticoagulation treatment after start of olaparib and when clinically indicated. For AEs of haemorrhage coagulation status and relevant monitoring of laboratory results is recommended.

From screening Part 2 onwards, should a patient develop nausea, vomiting and / or diarrhoea, then these symptoms should be reported as AEs and appropriate treatment of the event given.

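### Table 1 footnote h limits screening Part 2 to procedure-related SAEs, contradicting the wider Part 2 reporting rules in Sections 6.4.1, 6.5 and 7.7

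*Protocol*

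**What the plan says.** The screening schedule in Section 4, Table 1 has two columns. Part 1 covers BRCA testing, from the end of cycle 3 of the ongoing chemotherapy up to Day -28. Part 2 covers Day -28 to Day -1. The row "Adverse Events (from time of consent" is marked with footnote h under both columns, and footnote h states: "Only SAE's related to screening procedures will be collected at this visit".

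The text sections say something else about Part 2:

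- Section 6.4.1 opens with the general rule that "Adverse Events, including Serious Adverse Events, will be collected from time of signature of informed consent". It then makes one exception: "In screening part 1 only SAEs related to study procedures must be reported (AEs do not require reporting". It closes the exception with: "From screening Part 2 onwards - all AEs/SAEs must be reported".
- Section 6.5 applies the procedure-related limit to Part 1, and then: "From screening Part 2 onwards, all SAEs have to be reported, whether or not considered causally related to the investigational product". It extends this to study procedures as well.
- Section 7.7, also from Part 2 onwards, says that "should a patient develop nausea, vomiting and / or diarrhoea, then these symptoms should be reported as AEs".
- Section 6.4.11 limits the reporting of screening deaths to procedure-related ones in Part 1 only.

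The errata list of 15 November 2016 has two entries. Both concern footnote lettering in Table 2.

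**The concern.** Section 4.1 tells sites to carry out screening according to Table 1, so the table is an operative instruction. In Part 2 a site cannot follow footnote h and Section 6.4.1 together.

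Two things are at stake. The first is safety reporting. An SAE in Part 2 that has nothing to do with a screening procedure is reportable within 24 hours of awareness under Section 6.5, but is not collected under footnote h. If the patient then fails screening, she never reaches the Table 2 visits, and no later scheduled visit would pick the event up.

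The second is consistency of pre-treatment AE data. Olaparib starts within 8 weeks of the last platinum dose, and exclusion criterion 4 bars systemic chemotherapy only in the 3 weeks before treatment. Part 2 can therefore overlap recovery from chemotherapy, when residual nausea is plausible. The nature and patterns of nausea and vomiting AEs are a secondary objective (Section 2.2). AE records with onset dates and grades from before Day 1 help to separate carry-over from new onset. They help less if some sites of about 60 collect them and others do not.

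**Working it through.** No arithmetic bears on the contradiction, so the check is a comparison of passages.

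**Step 1. Does the footnote really apply to Part 2?** The row shows the marker in both columns. Elsewhere the same table separates its columns where that is meant: informed consent has footnote b in Part 1 and footnote i in Part 2, and the HRR tumour sample is marked in Part 1 only. As printed, footnote h governs Part 2.

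**Step 2. What does each passage require in Part 2?**

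- Table 1, footnote h: SAEs related to screening procedures, and nothing else.
- Section 6.4.1: all AEs and all SAEs.
- Section 6.5: all SAEs, whatever the causality. It makes no demand about non-serious AEs.
- Section 7.7: nausea, vomiting and diarrhoea as AEs. It makes no demand about other events.

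Each of the three sections conflicts with footnote h, each over a different range of events. Only Section 6.4.1 covers the whole range.

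**Step 3. Where does the text place the procedure-related limit?** Sections 6.4.1, 6.4.11 and 6.5 all attach it to Part 1 by name. No text section extends it to Part 2.

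**Step 4. Has it been corrected?** No. The errata list does not mention Table 1.

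**Step 5. What would a site following footnote h omit?** Every non-serious AE and every non-procedural SAE from Day -28 to Day -1, which is at most 28 days per patient. Under Section 4.1, patients with a tumour BRCA mutation already found by a local test may enter screening at Part 2. For them the limit would cover the whole of screening.

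**Step 6. What is collected regardless?** Part 2 takes medical and surgical history and relevant concomitant medications (Table 1). On Day 1 FLIE and FACT-O are scheduled, and AEs are collected without the limit (Table 2). FLIE asks about nausea and vomiting over the past 3 days. FACT-O includes a nausea item and a vomiting item with a 7-day recall (Appendix H). Nausea present just before treatment is therefore captured. What may be missing is the AE record, with onset and grade, for events earlier in Part 2.

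**The case against.** The strongest reply is that the intent is plain and this is a misplaced footnote letter. Section 6.4.1 states the rule and its Part 1 exception clearly, and Sections 6.4.11 and 6.5 agree. Footnote h speaks of a single visit, which fits one column. The table row itself says collection runs from consent. The principal investigator must ensure that staff know Section 6, and staff are trained on the Protocol before the first patient. On-treatment AE collection is not affected.

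Most of this stands. It shows which passage is probably out of line and makes it likely that many sites would report correctly. It does not remove the contradiction: the schedule that Section 4.1 sends sites to still gives the opposite instruction for Part 2.

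A reader might infer three stronger things that the documents do not support:

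- That Sections 6.4.1, 6.5 and 7.7 each demand all AEs and SAEs. Only Section 6.4.1 does.
- That the pre-treatment nausea baseline is lost. FLIE and FACT-O on Day 1, together with history and concomitant medications in Part 2, preserve much of it. Exclusion criterion 5, on persistent toxicity from earlier cancer therapy, also limits how much residual toxicity enters the study.
- That 28 days of AE data will be missing for every patient. That is the length of the window. Nothing in the Protocol shows how many sites would follow the footnote or how many events would fall in the window.

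**Conclusion.** The point holds as an internal contradiction in safety reporting. It is not a design choice, since the Protocol offers no reason for a narrower rule in Part 2 and three text sections say otherwise.

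Its size is bounded and modest. The exposed period is at most 28 days before first dose, for the planned 250 or so BRCAm patients, the HRRm cohort of about 25, and those who fail screening in Part 2. The most serious consequence is a non-procedural SAE in a Part 2 screen failure, which may go unreported. For enrolled patients the likelier consequences are late SAE reports and uneven pre-treatment AE records, including nausea and vomiting, which weakens one comparison behind a secondary objective. Co-primary PFS and the secondary time-to-event endpoints do not depend on it.

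This rests on one assumption: that at least some sites work from the schedule table when deciding what to record during screening. Section 4.1 directs them to it, but how many would do so is unknown.

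**What to change.** Reconcile the passages by keeping footnote h on the Part 1 column only. Give the Part 2 entry of the adverse event row its own footnote, stating that all AEs and SAEs are collected and referring to Section 6.4.1. Sections 6.4.1, 6.4.11, 6.5 and 7.7 need no change. The errata list would be a natural vehicle, since it already corrects Table 2 footnotes.

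The cost is one footnote and a note to sites. It adds no data beyond what Section 6.4.1 already requires. Sites that have been working from Table 1 should also be asked to check Part 2 records, screen failures included, for SAEs not yet reported.
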